The primary aim is to determine the efficacy of training with this exoskeleton and its ability to improve transfers to standing and sitting as assessed by the five times sit-to-stand test. A secondary aim will be to assess effects of the device during overground ambulation. Outcome measurements to investigate changes of knee range of motion and loading of the paretic limb will be accomplished using an instrumented goniometer; changes in limb loading will be monitored using a foot pressure mapping system; and stepping parameters will be recorded using the GaitRite carpet. An exploratory outcome of changes in energy expenditure during ambulation with and without the powered exoskeleton will be assessed from a 6-minute walking test using a portable metabolic cart. Another exploratory outcome measures of QOL will be determined using the SF-36 and

the Stroke Specific Quality of Life Scale. Additional exploratory outcomes to measure body composition, bone mineral density changes will be assessed using Dual X-ray Absorptiometry (DXA). Additional exploratory outcomes include measuring changes in cortical, corticospinal and spinal excitability in response to brain, spinal and peripheral nerve stimulation (PNS), and brain activation using electroencephalogram (EEG).

Baseline testing for both groups will be performed while ambulating without the device and prior to starting in the training program. The exoskeleton group will repeat testing within the first 3 sessions of the training program. Mid-point assessments will be obtained after 12 and 24 sessions of training. Post assessments will be obtained after 36 sessions of training. Retention will be assessed by repeating the assessments without the exoskeleton after 1 month of stopping the training program.

It is anticipated that longitudinal training with the device will increase number of squats achievable, increase knee flexion during swing, increase loading of the paretic limb, and induce symmetrical stepping. No immediate effect on energy expenditure by the device is expected however, a training effect is expected to demonstrate improvement in the energy cost of ambulation. Any gains observed during this study may not be retained, but as this device has the potential to be used in the home and community environment, justifying a prescription of this device for retention purposes may be warranted. Use of this device may also lead to improvement of QOL.

2. Specific Aims

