[figure not shown]

Figure 2: Box plot of oxygen uptake (VO₂) is displayed for each condition (SIT, STAND and WALK) and estimated maximal (Max) predicted VO₂ using predicted equations from leg and arm crank exercises. Significant differences ($p < 0.001$) were found between WALK compared with SIT and STAND (2).

[figure not shown]

Figure 3: Box plot of heart rate (HR) is displayed for each condition (SIT, STAND and WALK) and estimated maximal (Max) predicted HR. Significant differences ($p < 0.001$) were found between WALK compared with SIT and STAND. BPM = beats per minute (2).

benefit leading to increased use of the paretic limb even while not wearing the exoskeleton. With long-term use of this device, potentially this device could be used to combat muscle and bone loss in the paretic limb.

Research Design and Methods

Participants, Eligibility and Recruitment

Strategies: Fifteen persons with stable, chronic stroke (>6 months) will be recruited through the various outpatient clinics that treat Veterans with stroke at the James J Peters VA Medical Center (JJPVAMC). There were approximately 402 unique Veterans with chronic stroke who obtained services during 2018 at the JJPVAMC.

This would provide ample potential participants to prescreen 50 Veterans, as outlined in Table 1. It is expected that a portion (n~40) will express interest in signing informed consent, after which further screening will be performed. Candidacy will be determined based on the following inclusion and exclusion criteria: age between 18 and 89; weight under 250lbs, medically stable; and able to stand and initiate steps on their own with walking speed between 0.15-0.75m/s, but with chronic gait impairments such as reduced knee flexion and reduced time spent on the paretic limb during stance phase. A detailed list of the inclusion and exclusion criteria are presented in the Human Subject's section of this application. Because the effects of paralysis from stroke are believed to overpower the effects of age, gender or ethnicity, these demographic characteristics will not be restricted. A total of 15 participants are expected to enroll in the trial, however, to account for attrition, it is expected that 12 participants will complete the trial within the 2-year period.

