Randomization: Eligible participants will be randomized into either the exoskeleton group or control group. Block randomization will be used with a 2 to 1 ratio to result in 10 participants in the exoskeleton group and 5 participants in the control group (30). This ratio was chosen because future proposals will be focused on home and community use of the device, therefore more pilot data showing safety and feasibility is needed.

Description of Training Sessions: All participants will visit the JJPVAMC for 36 training sessions, 3 times per week for 3 months and will follow the recommendations of the American Heart Association (AHA) and American Stroke Association (ASA) (20). Those in the exoskeleton group will train using the Keeogo powered exoskeleton and those in the control group will train without the exoskeleton using their conventional assistive devices. Training sessions will be progressive, with duration to tolerance for a minimum of 20 minutes and a maximum of one hour. Training will consist of mobility activities affecting daily life including: walking; squatting (or getting in and out of a chair); bending, kneeling or stooping (for picking an item up off of the floor); and ascending and descending stairs. Sessions will be monitored and tailored to the individual, based on their functional ability and to ensure their safety. Exertion will be maintained at a level between 11-14/20 using the Borg scale (31), as per recommended by the AHA and ASA (20). All participants will be allowed to take as many breaks as needed during each session.

Technical Description of the Keeogo™ Powered Orthotic Exoskeleton: Those randomized into the powered exoskeleton group will be using the Keeogo™ (B-Temia Inc., Quebec City, QC, Canada) (32), which is a powered orthotic exoskeleton, designed for users who have difficulty ambulating and/or need assistance with movement of the knee (Figure 4). This device does not restrict movement and only provides assistance at the knee during extension and flexion during ambulation, standing up, sitting down and when ascending or descending stairs. It is not intended for use in those who have complete paralysis of their leg as it requires some active movement to assist with. The Keeogo™ weighs Protocol ASS-20-01
MIRB# 01929

Table 1: Recruitment efforts

	Year 1				Year 2				Totals
	Q1	Q2	Q3	Q4	Q1	Q2	Q3	Q4	
Pre-Screening	10	10	10	10	10	0	0	-	50
Screening	-	7	10	10	10	3	0	-	40
Enrollment	-	3	4	4	3	1	0	-	15

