The loading profile obtained from the F-Scan foot pressure system will be normalized over the gait cycle as percentage of gait cycle and percentage of body weight for each foot. The total area under the curve will be calculated to obtain a total load on each lower extremity. Peak measurements from heel strike and toe-off will be calculated from the curve along with mid stance where load is typically diminished. Maximum knee flexion angles from 10 continuous steps will be averaged for each limb.

Metabolic measurements (VO_2 , HR and RR) will be recorded as averages every minute. Energy cost of distance travelled will be calculated by dividing VO_2 normalized to body weight (ml/kg/min) by the distance traveled (ml/kg/m). The 6 values from the consecutive 1-minute recordings will be averaged for sitting and walking conditions.

Descriptive statistics will be employed for demographic and Fugl-Meyer data. A single group, repeated measures design will be employed in the experimental group to test the within-group effect of using the powered exoskeleton. A two group repeated measures design will be employed to test the between-group differences in outcomes. All outcome measurements will be analyzed using a mixed model ANOVA to determine significant main and interaction effects of group (control, experimental) and time (baseline, session 36, 1-month follow-up). A similar mixed model ANOVA will be used to determine significant main and interaction effects of the two conditions (without [w/o] and with [W] Keeogo exoskeleton) in the experimental group for the 3 time points (baseline, session 36, 1-month follow-up). Post hoc analyses of significant data will be performed using t-tests.

Table 3: Timeline of activities to complete the study

TIME LINE	Year 1				Year 2			
	Q1	Q2	Q3	Q4	Q1	Q2	Q3	Q4
Start-up Activities								
IRB & R&D	x				x			x
Staff Hiring and Training	x							
Purchase Equipment	x							
Database development	x							
Participant Screening	x	x	x	x	x	x		
Participant Enrollment	3	4	4	3	1	0		
Database management	x	x	x	x	x	x		
Abstract writing				x	x	x		
Manuscript writing					x	x		

Potential Difficulties and Limitations

The greatest hurdle in conducting investigations with devices is recruiting participants and completing the training as well as obtaining regulatory approval to conduct the study. Feasibility to enroll and complete the 15 participants is

Protocol ASS-20-01

MIRB# 01929

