subject is agreeable, a meeting time will be arranged to further explain the study, answer questions or address concerns prior to signing the consent forms. During this meeting, the PI (or designee) will read, verbatim, the consent form to the potential subject. After the consent form has been read, the PI (or designee) will ask if the potential subject has any questions, and to reiterate details of the protocol to insure they fully understand the commitments and is aware of their right to withdraw at any time without future prejudice. If there are no further questions, the consent form will be signed by the subject and the investigator. Copies of the signed and completed consent form will be entered in the electronic medical record system and a copy given to the subject. Every effort will be made, within the constraints of the enrollment criteria, to enroll women and persons of diverse ethnicities in the proposed research investigations.

Protection Against Risk.

The PI will oversee the conduct of data collection and will review all aspects of the data's quality during and immediately after data collection on a per subject basis. Efforts to minimize the previously described potential risks will be done by using a "Clinician Fitting Checklist" that will be provided to all study staff to ensure proper device fitting and training of staff to use the device properly. The checklist verifies placement of the device and that the appropriate device settings are being used. Completion of the fitting checklist will be performed prior to each training session; fit will be re-verified prior to performance of outcome assessments. In addition, the study physician will be available to field any questions that the participants may have regarding the study device, its effects, or their experiences. In the event of unexpected or expected adverse event, a report to the IRB will be completed in accordance with local policy. During the annual continuing review, the frequency and type of adverse events from the preceding year (and study duration) are reviewed. Under special circumstances, the IRB may request that the consent form be modified to reflect new potential risks or side effects. During our acute study, no participants exhibited or expressed any sign or symptom of an unanticipated side effect.

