All research protocols, informed consent forms, and case report forms are subject to random and/or planned annual audit and continuing review by the IRB and Research and Development Committee, which are accredited by the Association for the Accreditation of Human Research Protection Programs, Inc. The minimum number of procedures is being performed to effectively address the research objectives

Study participation can be terminated at any point during the investigation at the request of the participant or the PI. To minimize a breach against privacy after the time of consent, each subject will be assigned a code (unique subject identification number). Any data collected (digital and paper) pertaining to the study will be referenced and stored under this code. Digital data will be stored in a password-protected database on the VA network protected by the VA firewall. This firewall and encrypted network is protected by centralized antivirus software that is updated daily to prevent loss or compromise of data with malware. No raw or processed data are maintained on individual computers, or hard drives that may be lost or stolen. Every VA facility stores user's data on a local data center network that is backed up daily. Paper data will be stored in a locked file cabinet of the respective institutions. Study documents signed by the participant will have no reference to the participant number. A single digital key containing the name, contact information, and study coded number for all participants enrolled will exist for study administration and monitoring purposes only and be kept in a separate password protected database on the VA network behind the firewall. The PI and designated study staff will be the only individuals to have access to the password.

In the event of an unexpected adverse event during a study visit, appropriate medical intervention and care will immediately be sought in accordance with VA policies. A further explanation of adverse event reporting is provided in the subsequent section.

This research does not involve pregnant women, human fetuses and neonates, prisoners, children or individuals with diminished mental capacity. The possibility exists that economically or socially disadvantaged individuals

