Ensuring safety is a high priority, therefore, the following Data and Safety Monitoring Plan will be implemented. Adverse events and device malfunctions will be monitored on a session to session basis. All adverse events for all study participants including those that are anticipated or unanticipated will be recorded and submitted to the IRB in a timely and complete fashion. This safety information assists study management in identifying any untoward medical occurrence, thereby allowing: a) protection and safety of study participants, b) a greater understanding of the overall safety profile of the study treatments and therapeutic modalities, c) improvements in study design or procedures, and d) compliance with regulatory requirements. The PI will be responsible for reviewing the accuracy and completeness of all reported events, compliance with VA policies for reporting adverse events (AE), serious adverse events (SAE), Unanticipated Adverse Device Effects (UADE), and closely monitoring research participants at each study visit for any new SAEs. Any serious adverse event may lead to the change in study procedures to avoid any future occurrence of similar type of events. If any findings that may affect the participants' health or welfare, their primary care physician (PCP) will be notified of these findings.

The goals of this study have been outlined in the research plan. Weekly staff meetings will be scheduled to ensure study timeline and safety goals are met such as: IRB approval, database management and participant recruitment goals, participant compliance, adverse events, scheduling, etc. In the event there are some participants that are not reliable and are inconsistent with study appointments, the PI will have the ability to withdraw them from the study and they will be replaced.

The inclusion of women, minorities and/or children.

Every effort will be made, within the constructs of the inclusion and exclusion criteria, to identify and enroll women and persons of minority background in the proposed research investigation. Women, although comprising 50.7% of the total population in the United States, represent only 10% of Veterans. Under these circumstances, we do not anticipate an equal proportion of women to enroll in this investigation and realistically expect a similar proportion of women to participate in the project. The racial and ethnic background of the

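### Poor attenders may be withdrawn and replaced, and those who leave before session 36 give the planned analyses no post-baseline value: keep assessing them in their randomised arm, and add rather than substitute participants

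*Combined protocol and SAP*

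**What the plan says.** The rule is in the Data and Safety Monitoring Plan text of section 04 (Human Subjects). For participants who are unreliable in keeping appointments, "the PI will have the ability to withdraw them from the study and they will be replaced". The withdrawal is from the study, not only from training. Section 04, Protection Against Risk, adds a general clause: "Study participation can be terminated at any point during the investigation at the request of the participant or the PI".

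The Description of Data and Statistical Analyses plans a between-group model of "main and interaction effects of group (control, experimental) and time (baseline, session 36, 1-month follow-up". It also states: "A single group, repeated measures design will be employed in the experimental group to test the within-group effect of using the powered exoskeleton". The with/without-device model in that arm uses the same three time points. The opening summary says that "Mid-point assessments will be obtained after 12 and 24 sessions of training", and Table 2 schedules the primary five-times-sit-to-stand test (5xSTS) at both. Neither model includes those visits.

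The documents give no attendance threshold, no assessment after withdrawal, no analysis set and no rule for which arm a replacement joins. On numbers, 15 are to enrol and "it is expected that 12 participants will complete the trial within the 2-year period".

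**The concern.** Nearly all appointments are the 36 training sessions, which follow randomisation, so the rule acts mainly on behaviour after allocation. A person removed before session 36 has only a baseline among the modelled time points, and someone else takes the place. The people who supply change scores are then partly chosen by attendance.

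Two analyses are exposed. The randomised comparison is distorted if removal, or the link between attendance and outcome, differs by arm. That is plausible when only one arm trains in a powered device, but the documents do not show it. The exoskeleton arm's change over time can shift even if both arms lose people equally.

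Retention reporting is affected too. The Randomization paragraph justifies the 2:1 ratio because "more pilot data showing safety and feasibility is needed", and a completion rate means little if replaced people may or may not be counted.

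**Working it through.** **1. The plan's own figures.** Table 1 enrolment: 3+4+4+3+1 = 15. Completers: 0+2+3+3+3+1 = 12. Loss: 3/15 = 20%. These reproduce; the table budgets for losses and shows no replacements.

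**2. What a person withdrawn before session 36 contributes.** A classical repeated-measures ANOVA drops the case. A likelihood-based mixed model keeps the baseline, which adds little. Take 8 v 4 completers (assumed split of the 12) and an assumed equal correlation of 0.5 between visits, so that the SD of change is √(2×0.5) = 1. The standard error of the group difference in change is √(1/8+1/4) = 0.612 SD for completers only, 0.597 with the three baseline-only records, and √(1/10+1/5) = 0.548 if all 15 are assessed.

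**3. Between-group shift.** The documents give no rate of removal by the investigator, so this is an illustration. Assumptions: the lowest k of n on a standard normal attendance score are removed and replaced by unselected people; attendance–outcome correlation r = 0.3 to 0.5. The shift in an arm's mean attendance score, from 400,000 simulated arms, is 0.154 (1 of 10), 0.254 (2 of 10) and 0.232 (1 of 5). The outcome shift is r times this. Positive means favouring the exoskeleton arm.

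| Removed, exoskeleton v control | Score difference | × 0.3 | × 0.5 |
|---|---|---|---|
| 2 of 10 v 0 of 5 | 0.254 | +0.08 SD | +0.13 SD |
| 0 of 10 v 1 of 5 | −0.232 | −0.07 SD | −0.12 SD |
| 2 of 10 v 1 of 5 | 0.254 − 0.232 = 0.022 | +0.01 SD | +0.01 SD |

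For expected removal rates p of 30% v 10% (assumed, not from the protocol), the shift is r × [φ(z at 0.30) − φ(z at 0.10)], where φ is the standard normal density: 0.3477 − 0.1755 = 0.172. Times 0.3 to 0.5, this is 0.05 to 0.09 SD. It is zero if p and r are the same in both arms.

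**4. Against the noise.** With a standard error of 0.548 SD, a shift of 0.08 to 0.13 SD is 0.14 to 0.23 standard errors. By normal approximation, a two-sided 5% test would reject at about 5.2% to 5.6% under no effect.

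**5. Exoskeleton arm's change over time.** 1 of 10 removed: 0.154 × 0.3 to 0.5 = 0.05 to 0.08 SD. 2 of 10: 0.08 to 0.13 SD. The standard error of the arm mean is √(1/10) = 0.316 SD.

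**6. What sessions 12 and 24 could recover.** Suppose 2 exoskeleton and 1 control participants leave after both visits. The standard error then moves as follows:

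- equal correlation 0.5: 0.597 to 0.589, full data 0.548; recovers 0.008/0.049 = 16% of the gap;
- equal correlation 0.7: 0.467 to 0.457, full data 0.424; 0.010/0.043 = 23%;
- first-order autoregressive 0.8: 0.590 to 0.566, full data 0.541; 0.024/0.049 = 49%.

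Someone removed before session 12 gains nothing from these visits. Table 2 shows no quality-of-life, DXA or neuronal-excitability measurement at them.

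**7. Denominator, hypothetical.** If three people left and were replaced, and every replacement finished, completion would be 15/18 = 83% of everyone randomised, or 15/15 = 100% with the replaced people left out.

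**The case against.** The strongest reply is that this matters little in a 15-person pilot. The rule is discretionary, the protocol reports from experience that retention is seldom a problem, and the illustrated shift is small beside the standard error and nearly vanishes when removal is equal. The correlations and the removal of exactly the lowest attenders are assumptions. All of that stands, and it limits the point to a modest one. It does not remove it: outcomes never collected cannot be recovered later, and the remedy is a few sentences.

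Four stronger readings are tempting and are not supported.

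- A reader might infer that the investigator could remove people in the light of their results, because data are reviewed "during and immediately after data collection on a per subject basis". That sentence is about data quality. No blinding of the investigator is described, but nothing shows removal guided by outcome.
- A reader might take 83% v 100% completion as a forecast. The three expected losses are general attrition, and Table 1 replaces none of them.
- A reader might divide by the retained fraction in the 30% v 10% case and get 0.09 to 0.15 SD. That describes an arm in which nobody is replaced, or in which replacements pass the same attendance screen. With unselected replacements it is 0.05 to 0.09 SD.
- A reader might think every planned result is affected. The same-visit contrast with and without the device is within person, so unequal removal between arms does not bias it. Adverse events are recorded for all participants.

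**Conclusion.** The point holds as a design choice worth correcting. Followed as written, the withdrawal rule and the three-time-point models can restrict the group-by-time comparison and the exoskeleton arm's change over time to people selected on attendance after randomisation. That reading rests on the text alone.

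The size and direction of any bias cannot be known from the documents. Under the stated assumptions it is probably modest, and for the between-group comparison it requires removal, or its relation to outcome, to differ by arm. It is not a reason to doubt the trial as a whole.

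**What to change.** **Main change (Data and Safety Monitoring Plan, and consistently in Protection Against Risk).** State that participants who miss or stop training, unless they withdraw consent or are ended for safety, are still invited to the post-training and 1-month assessments and are analysed in their randomised arm. Set these visits by the calendar weeks in Table 2 (weeks 12–13 and 16), because a poor attender may never reach session 36. Any extra participant takes the next slot on the randomisation list and is added to, not substituted for, those who left. Report attendance, withdrawals with reasons, and retention by arm over everyone randomised.

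**Secondary change (Description of Data and Statistical Analyses).** For outcomes measured after sessions 12 and 24, such as 5xSTS, include those data in a likelihood-based mixed model with a simple covariance. An unstructured matrix for five time points needs 5×6/2 = 15 parameters, with 15 people. This helps only those who reach these sessions and recovers only part of the loss, so it does not replace the main change.

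**Cost.** Short wording changes and attempts at two visits already scheduled. Some attempts will fail, and the estimate may be slightly less favourable than one among good attenders. Extra participants use training slots, as replacements already would. With 18 people, for example, four at a time needs 5 cohorts × 4 months = 20 months, against the 18 that Potential Difficulties and Limitations allows; at the five-at-a-time capacity stated there, 4 cohorts × 4 months = 16 months.
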